NCI supplied agent may be requested by the eligible participating investigator (or their authorized designee) at each participating institution. The CTEP assigned protocol number must be used for ordering all CTEP supplied investigational agents. The responsible investigator at each participating institution must be registered with CTEP, DCTD through an annual submission of FDA form 1572 (Statement of Investigator), NIH Biosketch, Agent Shipment Form, and Financial Disclosure Form (FDF). If there are several participating investigators at one institution, CTEP supplied investigational agents for the study should be ordered under the name of one lead participating investigator at that institution. Patients must be enrolled prior to ordering study agent since no starter supplies are being provided. If expedited ordering is required, sites should provide express courier information through the Online Agent Order Processing (OAOP) application.

Note: No starter supplies will be provided. Drug orders of trametinib should be placed with CTEP after enrollment on ADVL1521 with consideration for timing of processing and shipping to ensure receipt of drug supply prior to start of protocol therapy. If expedited shipment is required, sites should provide an express courier account through the Online Agent Order Processing (OAOP) application. Provide the patient ID number in the comment box when submitting an order request.

Submit agent requests through the PMB Online Agent Order Processing (OAOP) application. Access to OAOP requires the establishment of a CTEP Identity and Access Management (IAM) account and the maintenance of an "active" account status, and a "current" password, and active person registration status. For questions about drug orders, transfers, returns, or accountability, call or email PMB any time. Refer to the PMB's website for specific policies and guidelines related to agent management.

Agent Accountability

Agent Inventory Records:

The investigator, or a responsible party designated by the investigator, must maintain a careful record of the receipt, dispensing and final disposition of all agents received from the PMB using the appropriate NCI Investigational Agent (Drug) Accountability Record (DARF) available on the CTEP forms page. Store and maintain separate NCI Investigational Agent Accountability Records for each agent, strength, formulation and ordering investigator on this protocol.

Investigator Brochure Availability

7.0 EVALUATIONS/MATERIAL AND DATA TO BE ACCESSIONED

Timing of protocol therapy administration, response assessment studies, and surgical interventions are based on schedules derived from the experimental design or on established standards of care. Minor unavoidable departures (up to 72 hours) from protocol directed therapy and/or disease evaluations (and up to 1 week for surgery) for valid clinical, patient and family logistical, or facility, procedure and/or anesthesia scheduling issues are acceptable (except where explicitly prohibited within the protocol).

7.1 End of Therapy & Follow-up

STUDIES TO BE OBTAINED	End of Therapy	Progressive Disease
History	X	
Physical exam with VS	X	
Ht, Wt, BSA	X	

Performance status	X	
Pregnancy test	X	
CBC, differential, platelets	X	
Electrolytes including Ca ⁺⁺ , PO ₄ , Mg ⁺⁺	X	
Creatinine, SGPT (ALT), bilirubin	X	
Total protein/albumin	X	
Bone marrow evaluation	X	
JMML panel using mutation allele burden	X	X
Genomic, Epigenomic and Functional assays*	X	X

*if the patient consented

See COG Late Effects Guidelines for recommended post treatment follow-up:

<http://www.survivorshipguidelines.org/>

Note: Follow-up data are expected to be submitted per the Case Report Forms (CRFs) schedule.

7.2 Retrospective Central Pathology Review

7.2.1 Requested Materials

Please send the following materials for retrospective pathology review at baseline collection, at the end of Cycles 1 and 2, and when subsequent bone marrows are collected for review:

- Bone marrow biopsy (if unavailable; submit a bone marrow aspirate clot): 1 H& E stained glass slide
- Bone marrow aspirate smear: 1 or 2 stained (e.g. Wright's Giemsa) aspirate smears
- Peripheral blood smear: 1 stained smear
- A copy of the CBC report from the date of marrow collection

7.2.5 Cytologic Slides- Storage/Return

Cytologic slides will be retained at the UCSF Hematopathology lab indefinitely, unless the institution requests their return.

7.3 **Mutant Allele Burden Measurement REQUIRED**

The mutant allele burden assay encompasses the DNA sequencing of all exons in each of the following genes: *NRAS*, *KRAS*, *RRAS2*, *PTPN11*, *CBL*, *NF1*, *SETBP1*, *SH2B3*, *ASXL1*, and *JAK3*. The assay is quantitative and is intended to monitor the allele burden of one or more previously uncovered mutations in a patient to assess for minimal residual disease. See [Appendix V](#) for details regarding the determination of pathogenicity.

When a patient enrolls on study, send an email to [contact] with a copy to the COG assigned Study Research Coordinator, to receive a specimen collection kit.

7.3.1 **Sample Collection and Handling Instructions**

A peripheral blood sample will be collected at the time points described below. Each sample will be utilized for the purpose of mutant allele burden measurement.

Sampling Schedule and Collection

Peripheral blood samples will be obtained at the following time points:

- A single sample collected at any time between Day -14 through Day 0, before Cycle 1 (if sent as fee-for-service, can be collected up to 30 days prior to treatment)
- Day 28 of Cycle 1
- Day 1 of every odd Cycle (3, 5, 7, etc....)
- Progressive disease (when applicable)
- End of Treatment

Sample Processing and Labeling

Collect peripheral blood samples of approximately 2-4 mL in Sodium (Na) Heparin green top tubes. Invert 5 times to ensure mixing of the anticoagulant and blood. Peripheral blood should be collected at every Mutant Allele Burden Measurement timepoint listed above.

Collect 4 buccal swabs for each cheek (8 total) by gently rolling the swab along the inside of each cheek 10 times. Place each swab inside a separate tube making sure not to touch the tips. Patient should not have any food inside the mouth at the time of collection. Buccal swabs will only be collected at the initial time point (Day -14 through Day 0, before Cycle 1).

Each tube and swab must be labeled with the patient's COG I.D., study number (ADV1521), and the date and time the sample was drawn. Data should be recorded on the Mutant Allele Burden Measurement Specimen Transmittal Form, which must accompany the sample(s).

7.3.2 **Sample Shipping Instructions**

The samples should be shipped to the UCSF Molecular Diagnostics

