3.2.4 Prior Therapy

Patients must have fully recovered from the acute toxic effects of all prior chemotherapy, immunotherapy, or radiotherapy prior to study enrollment.

- a. Myelosuppressive chemotherapy: Patients must have completely recovered from all acute toxic effects of chemotherapy, immunotherapy or radiotherapy prior to study enrollment. At least 14 days must have elapsed since the completion of cytotoxic therapy, with the exception of hydroxyurea.
- Note:** Cytoreduction with hydroxyurea can be initiated and continued for up to 24 hours prior to the start of protocol therapy.
- b. Hematopoietic growth factors: At least 14 days after the last dose of a long-acting growth factor (e.g., pegfilgrastim) or 7 days for short-acting growth factor. For agents that have known adverse events occurring beyond 7 days after administration, this period must be extended beyond the time during which adverse events are known to occur.
- c. Biologic (anti-neoplastic agent): At least 7 days must have elapsed since completion of therapy with a biologic agent. For agents that have known adverse events occurring beyond 7 days after administration, this period prior to enrollment must be extended beyond the time during which adverse events are known to occur.
- d. Monoclonal antibodies:
- i. At least 30 days after the completion of any type of immunotherapy, e.g. tumor vaccines.
 - ii. At least 3 half-lives must have elapsed since prior therapy that included a monoclonal antibody. (See posting of half-lives for commonly used monoclonal antibodies on the DVL homepage (<https://members.childrensoncologygroup.org/Disc/devtherapeutics/default.asp>)).
- e. Radiotherapy:
- i. ≥ 2 weeks must have elapsed since local palliative XRT (small port)
 - ii. ≥ 6 months must have elapsed if prior craniospinal XRT was received, if $\geq 50\%$ of the pelvis was irradiated, or if TBI was received
 - iii. ≥ 4 weeks must have elapsed if other substantial bone marrow irradiation was given.
- f. Stem Cell Transplant or Rescue without TBI: No evidence of active graft vs. host disease and ≥ 3 months must have elapsed since transplant. ≥ 4 weeks must have elapsed since any donor lymphocyte infusion.

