***For Day 1 observations, g- p samples may be collected up to 14 days prior to the start of therapy.**

%JMML panel for mutant allele burden may be collected up to 14 days prior to the start of therapy if sent as a correlative biology study on this trial or up to 30 days prior to the start of therapy if the same test was ordered as fee-for-service and processed at UCSF.

- a. Physical exam (including VS with triplicate BPs), and adverse events
- b. Concomitant medications
- c. Performance status
- d. CBC, differential, platelets (see [Section 7.2](#) for details regarding Central Review).
- e. Electrolytes including Ca^{2+} , Mg^{2+} , and PO_4 , BUN and creatinine, creatine kinase bilirubin (total and direct), AST, and ALT
- f. Dermatologic exam. Performed by the treating physician (or dermatologist, at the discretion of the investigator). If possible, the same physician should perform each exam throughout the study. Photographs of suspect lesions at baseline are recommended. Photographs and/or biopsies of any new or changing lesions recommended at subsequent on-study visits
- g. An age-appropriate ophthalmologic examination with a funduscopy evaluation that avoids any sedation to be performed by an ophthalmologist at baseline. This includes a Snellen examination (if age appropriate as determined by the investigator). See [Section 4.1.6](#)
- h. Peripheral blood smear (See [Section 7.2](#) for details regarding Central Review)
- i. BMA/clot section or biopsy and aspirate smear (see [Section 7.2](#) for details regarding Central Review)
- j. BMA cytogenetics and FISH (It is recommended that cytogenetics/FISH be performed by a COG-approved laboratory)
- k. For patients that consent, collect bone marrow for Genomic, Epigenomic, and Functional assays (see [Section 7.3.3](#))
- l. Echocardiogram or MUGA
- m. ECG
- n. CSF for cell count, cytospin (lumbar puncture only required if clinical suspicion of CNS involvement)
- o. Pregnancy test. Female patients of childbearing potential require a negative pregnancy test
- p. Imaging (CT or MRI) of chloroma (if present)
- q. For patients that consent, collect peripheral blood for Pharmacokinetic and Pharmacodynamic studies (see [Section 7.4.1](#))
- r. Peripheral blood sample for the JMML panel using mutant allele burden (see [Section 7.3.1](#))

This listing only includes evaluations necessary to answer the primary and secondary aims. OBTAIN OTHER STUDIES AS REQUIRED FOR GOOD CLINICAL CARE.

Comments

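### The fee-for-service exception lets the only baseline mutant allele burden sample predate the end of prior therapy, so change before Day 1 cannot be separated from change on trametinib

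*Combined protocol and SAP*

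**What the plan says.** Section 7.3.1 defines the baseline for the mutation panel as "A single sample collected at any time between Day -14 through Day 0, before Cycle 1", with the exception "if sent as fee-for-service, can be collected up to 30 days prior to treatment". The Cycle 1 observation list in Section 4.2.2 repeats the exception and ties it to one laboratory: "or up to 30 days prior to the start of therapy if the same test was ordered as fee-for-service and processed at UCSF". The next scheduled sample is Day 28 of Cycle 1.

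The other baselines are tighter. Section 3.2 requires the marrow within 2 weeks before therapy, and Section 4.2.2 limits items g to p to 14 days. The buccal swabs in Section 7.3.1 are confined to Day -14 to Day 0 without exception.

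The washouts are in Section 3.2.4, whose opening sentence sets study enrollment as the reference point:
- Cytotoxic therapy: "At least 14 days must have elapsed since the completion of cytotoxic therapy, with the exception of hydroxyurea".
- Biologic agents: "At least 7 days must have elapsed since completion of therapy with a biologic agent".
- Hydroxyurea: "Cytoreduction with hydroxyurea can be initiated and continued for up to 24 hours prior to the start of protocol therapy".
- Donor lymphocytes: "≥ 4 weeks must have elapsed since any donor lymphocyte infusion".

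Section 3.1.5 allows a projected start up to 7 business days after enrollment. Section 6.1 says drug is ordered only after enrollment.

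The notes to Appendix III, Table 1 make this assay the basis of molecular response. Under Section 10.2, gCR gives an overall CR even with clinically stable disease, and gPD gives an overall PD whatever the clinical response. Section 9.8 analyses allele burden descriptively and has no rule on the age of the baseline.

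**The concern.** A 14-day limit on baseline samples, combined with a 14-day washout, keeps the baseline after the end of cytotoxic therapy. The exception breaks that link for the one variable that decides genetic response. With a single baseline and no further sample until Day 28 of Cycle 1, a change caused by prior therapy between the early draw and Day 1 looks the same as a change on trametinib.

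Two analyses depend on this sample. Aim 1.2.3 uses the course of the allele burden, so any early change enters it. The primary endpoint uses the sample in two ways. Table 1 lets a molecular CR be assessed only if an anomaly was there before treatment, and a stale positive sample can satisfy that for a patient who was already negative on Day 1. In the other direction, a JMML mutation gained between the early draw and Day 1 counts as newly acquired, hence gPD and overall PD. PD ends protocol therapy (Section 8.1), and Section 9.3 counts only responses reached before PD. The bias can therefore run for or against the drug.

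**Working it through.** **1. Calendar overlap.** Let g be the calendar days from enrollment to first dose and W the washout to enrollment. Prior therapy can end as late as Day -(W + g), so a Day -30 sample predates that by 30 - (W + g) days. Seven business days span at most 11 calendar days, ignoring public holidays, so g runs from 0 to 11.

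| Prior therapy at its minimum washout | W | g = 0 | g = 11 |
|---|---|---|---|
| Cytotoxic | 14 | 30 - 14 = 16 days | 30 - 25 = 5 days |
| Biologic agent | 7 | 30 - 7 = 23 days | 30 - 18 = 12 days |
| Donor lymphocytes | 28 | 30 - 28 = 2 days | none (gone once g = 2) |

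For comparison, a standard Day -14 sample overlaps cytotoxic therapy by at most 14 - 14 = 0 days and a biologic agent by at most 14 - 7 = 7 days. Each further day of washout or delay removes one day of overlap.

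**2. What is credited for response.** Table 1 defines no partial molecular response, and in Table 2 anything short of gCR without progression is gSD. With gSD, an overall PR needs cCR or cPR, and the clinical variables do not use this sample. A false CR therefore needs every acquired mutation to be gone and the karyotype to be normal. A partial fall in allele burden affects Aim 1.2.3 only.

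**3. The plan's own design figures.** For the 10 + 10 design in Section 9.2 (stop at 0 of 10; effective at 3 or more of 20):

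P(effective | p) = sum over x = 1 to 10 of b(x; 10, p) × P(Bin(10, p) ≥ 3 - x).

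This gives 0.0686 at p = 0.05 and 0.8820 at p = 0.25. Early stopping at 5% is 0.5987 and expected size 14.01. The stated 0.069, 0.882, 0.599 and 14.01 are reproduced.

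**4. Illustration of sensitivity.** This is an assumption and is not in the documents. Let q be the share of non-responders falsely scored CR. The null rate becomes 0.05 + 0.95q.

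| q | Apparent null rate | Type I error |
|---|---|---|
| 0 | 0.0500 | 0.069 |
| 1% | 0.0595 | 0.103 |
| 2.5% | 0.0738 | 0.165 |
| 5% | 0.0975 | 0.285 |

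Here q is the fee-for-service share times the chance of complete clearance between the early sample and Day 1. For example, q = 1% is 50% × 2%, and q = 5% is 50% × 10%. Neither factor is given in the plan.

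**The case against.** The strongest reply is that this is a convenience exception with a small effect. It is limited to the same test at the same laboratory. Marrow and cytogenetics stay within 14 days. Patients must have persistent disease after prior therapy, so complete clearance just before Day 1 should be uncommon. Because drug is ordered only after enrollment, a same-day start is impractical and the 16-day figure is an upper limit. All of this stands. It narrows the problem without removing it: the overlap is still about 5 days at the longest delay, and Section 3.2.3.1 lets persistence rest on clinical symptoms alone, so a detectable mutation at start is not guaranteed.

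A second reply is that Table 2 words gCR as a state, so a fresh negative sample would not by itself prevent a false CR. That is fair. The fix must say that the reference sample also governs Table 1's requirement of an abnormality before therapy.

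A third is that hydroxyurea may continue until 24 hours before therapy, so even the standard window is not free of prior treatment. That is also right, and the fix should not reject early samples because of hydroxyurea alone.

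Stronger readings are tempting. A reader might infer that 16 of the 31 allowed days (52%) are contaminated. That assumes a same-day start at the minimum washout, and it is a share of calendar days, not a probability for any patient. A reader might also note that one false responder in the first 10 raises the chance of declaring the drug effective to 0.245. The arithmetic is right, but it holds for a false responder from any cause, and the documents give this event no probability.

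**Conclusion.** The gap is real and worth closing as a cheap improvement. At the minimum washout, the only baseline allele-burden sample can predate the end of cytotoxic therapy by about 5 to 16 days, and the end of a biologic agent by 12 to 23 days. The donor lymphocyte overlap, at most 2 days, is minor. The effect on Aim 1.2.3 is direct. The effect on the primary endpoint passes only through complete genetic clearance or a newly gained mutation, and it can go either way.

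The documents do not support a claim that prior-therapy effects will generally be credited to trametinib, or that the type I error actually exceeds 0.069. The range 0.103 to 0.285 rests wholly on the assumed 1% to 5%. The overlap figures rest on reading the 14 and 7 days as counted to enrollment, on 7 business days being at most 11 calendar days, and on patients at the minimum washout whose baseline came by the fee-for-service route.

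**What to change.** In Sections 7.3.1 and 4.2.2, accept a fee-for-service sample from before Day -14 as the baseline only if it was drawn after the last dose of prior cytotoxic therapy (other than hydroxyurea), demethylating therapy or biologic therapy, and after any donor lymphocyte infusion. Otherwise draw the standard 2-4 mL sample between Day -14 and the first dose, after that therapy has ended. State that this sample is the reference for the molecular precondition in Table 1, for gCR and gPD, and for Section 9.8. The washouts themselves need no change.

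For patients already enrolled, add a sensitivity analysis of response and allele burden restricted to baselines drawn after prior therapy. It needs only the draw date and the last-dose date.

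The cost is one sentence in two places and a repeat panel in a few patients, with the tube taken at a blood draw that already happens before dosing.

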7.4 Correlative Biology Studies

Please note that no more than 3 mL/kg of blood or bone marrow should be drawn on any one day for patients <1 year of age. For patients >1 year of age, no more than 2 mL/kg of blood or bone marrow should be drawn on any one day.

7.4.1 Pharmacodynamic (PD) and Pharmacokinetic (PK) Studies OPTIONAL

For patients who consent, peripheral blood samples will be collected for the purpose of determining trametinib concentration. When a patient is being considered for PD and PK studies, send an email to [contact] to receive a kit with supplies for blood collection with a copy to the COG assigned Study Research Coordinator.

Pharmacodynamic Studies: Plasma inhibitory assays will be performed to indirectly assess levels of MEK inhibition in patient samples. Phospho-flow cytometry will also be performed on samples to assess changes in intracellular and extracellular signaling after exposure to trametinib.

Pharmacokinetic Studies Trametinib will be extracted from plasma and will be quantified by internal standardization and HPLC-MS/MS methodology. Peak areas will be generated and peak area ratios will be used to calculate trametinib concentrations in each sample.

7.4.1.1 Sample Collection and Handling Instructions

Sampling Schedule and Collection

Blood samples will be obtained at the following time points during Cycle 1:

- Day 1, hours 0 and 4
- Day 15, hours 0 and 4

Sample Processing and Labeling

Collect blood samples of approximately 4 mL in a K2 EDTA Vacutainer and invert to ensure mixing of the anticoagulant and blood. Store the blood samples on wet ice for approximately 10 minutes. Centrifuge (refrigerated centrifuge) at approximately 2000g for 10 minutes at 4°C. Transfer the plasma immediately after centrifugation to an appropriately labeled 1.8 mL NUNC storage tube and store at -80°C. Plasma samples on day 1 and 15 can be stored at -80°C, and batched for shipment on dry ice at the end of cycle 1 on day 28 along with smart tubes (see section 7.4.2.1). Any remaining blood in the EDTA tubes after removing the plasma should be shipped room temperature on the day of collection.

Each tube must be labeled with the patient's COG I.D., study number (ADV1521), and the date and time the sample was drawn. Data should be recorded on the PD and PK Specimen Transmittal Form, which must accompany the sample(s).

7.4.2 Genomic, Epigenomic and Functional Studies **OPTIONAL**

We will perform exome sequencing, RNA seq, methylation profiling, and CG-CSF hypersensitivity assays at diagnosis, at the end of Cycles 1 and 2, and disease progression (if applicable). We aim to determine whether genomic, transcriptomic, or epigenetic changes occur as a result of treatment with trametinib.

When a patient is being considered for these optional studies, send an email to [contact] with a copy to the COG assigned Study Research Coordinator, to receive a kit with supplies for bone marrow collection.

7.4.2.1 **Sample Collection and Handling Instructions**

For patients who consent, bone marrow and peripheral blood samples will be collected at the time points described below. Samples will be used to determine whether genomic, transcriptome, or epigenetic changes occur as a result of trametinib treatment.

If available, please send bone marrow slides (unstained aspirate smears or 5 unstained FFPE recuts) from the original diagnosis of JMML. DNA will be extracted for the purpose of mutation analysis and paired sequencing with relapse samples.

If a patient consents to optional studies, leftover DNA from buccal swabs collected as part of the mandatory Mutant Allele Burden Measurement test will be used as a germline control for next generation sequencing for research.

Sampling Schedule and Collection

Bone marrow and peripheral blood samples will be obtained at each of the following time points:

- Any time point between Day -14 through Day 0 before Cycle 1 therapy
- Day 28 of Cycle 1
- Day 28 of Cycle 2
- Progressive disease (when applicable)

Sample Processing and Labeling

Collect bone marrow samples of approximately 5-10 mL in Sodium (Na) Heparin green top tubes. Invert 5 times to ensure mixing of the anticoagulant and bone marrow.

Collect peripheral blood samples of approximately 5-10 ml in Sodium (Na) Heparin green top tubes and invert to ensure mixing of the anticoagulant and blood. Transfer 1ml from the Sodium Heparin tube(s) into three separate Smart Tubes (1ml in each of the three Smart Tubes). Smart Tubes collected before and during cycle 1 should be stored at -80°C and batched for shipment at the end of cycle 1 on day 28 along with NUNC tubes (see [section 7.4.1.1](#)). Any remaining blood in the Sodium Heparin tubes should be shipped same day at room temperature.

Smart tubes collected during cycle 2 and at progression (if applicable) should be stored at -80°C and shipped on dry ice as soon as possible.

Please see the ADV1521 protocol page for additional Smart Tubes instructions.

Each tube must be labeled with the patient's COG I.D., study number (ADV1521), and the date and time the sample was drawn. Data should be recorded on the Biologic Studies Specimen Transmittal Form, which must accompany the sample(s).

